10. STATISTICAL CONSIDERATIONS

10.1 Study Design/Endpoints/ Determination of Sample Size

This is a phase II trial. Primary objective is to determine the overall response rate. Historically ORR with single agent Nivolumab in CRC is <5% and Metformin and Nivolumab combination will have ORR of 15%. Simon's MinMax two stage design is employed for the study with power of 80% and alpha of 0.1. If there is 1 response in first 18 patients in the first stage of the study, then it will proceed with second stage to enroll total of 28 patients. If there are 3 or more responders out of the 28 patients then it would be positive study. This will enable us to evaluate clinical endpoints (ORR, CEA, RFS, OS) as well as evaluate the impact on immune biomarkers.

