10.2 Statistical and Analytical Plans

Summary statistics will be presented for all safety, efficacy and biomarker parameter analyses. The purpose of these analyses is hypothesis generating. Various exploratory statistical tests may be applied to data generated from this trial to generate hypotheses to be tested in subsequent trials. In general, data for continuous parameters will be presented using descriptive statistics including sample size, mean, and median; standard deviation; and minimum and maximum. Categorical parameters be displayed using counts and percentages. Toxicities will be presented as worst toxicity per patient and will be reported as percent toxicity.

Objective response rate will be calculated as proportion (Responders/Total patients) along with 95% confidence intervals using the Clopper-Pearson method. Chi-square test or Fisher's exact test will be used to compare the efficacy in term of response rate, biochemical response (CEA) between the different groups stratified by biomarkers or other factors, respectively. Logistics regression

model will be further employed to test the adjusted effect of biomarkers on the response rate after adjusting for other clinical factors and demographic factors.

For progression free survival, progression or death from any cause will be defined as the event. Patients will be censored at time of last follow-up. For overall survival, death from any cause will be defined as the event. Patients will be censored at time of last follow-up. Overall survival (OS) and progression free survival (PFS) rates of two patient groups stratified by response or other factors will be estimated with the Kaplan-Meier method and compared between different groups using the log-rank test, respectively. The PFS and OS of each patient group at specific time points, such as 6 months, 1 year, 3 year, and 5 year, etc. will be also estimated alone with 95% CI. Cox proportional hazards models will be further used in the multivariable analyses to assess adjusted effect of response on the patients' OS and PFS after adjusting for other factors. Interaction terms between these factors will also be tested for statistical significance. The proportional hazards assumption will be evaluated graphically and analytically with regression diagnostics. Violations of the proportional hazards assumptions will be addressed by use of time-dependent covariates or extended Cox regression models.

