For the biomarker study, descriptive statistics will be first used to summarize biomarker endpoints, including analyses of tumor biopsies. Biomarker data will also be displayed graphically, where appropriate. Depending on whether data is normally distributed, t-test or Wilcoxon rank sum test will be used to compare each biomarker between any two groups stratified by response or other factors, respectively. General linear model (GLM) will be used to compare each biomarker between responders and nonresponders with and without adjusting for other factors. Logistics regression model will be further employed to test the adjusted effect of biomarker on the response rate after adjusting for other factors.

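### Covariate-adjusted logistic models of response are planned on about 1 to 4 expected responders with no sparse-data method, and response is used as a grouping for PFS and OS without a landmark.

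*Combined protocol and SAP*

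**What the plan says.** Section 10.1 fixes the size of the trial and the rates: "Historically ORR with single agent Nivolumab in CRC is <5" per cent, and "Metformin and Nivolumab combination will have ORR of 15" per cent. The design is stated as "Simon's MinMax two stage design is employed for the study with power of 80% and alpha of 0.1", with 18 patients in stage 1, 28 in total, and a positive result at 3 or more responders.

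Section 10.2 then plans three kinds of model that involve response:

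- A logistic "model will be further employed to test the adjusted effect of biomarkers on the response rate after adjusting for other clinical factors" and demographic factors.
- In the biomarker paragraph: "Logistics regression model will be further employed to test the adjusted effect of biomarker on the response rate", again adjusted for other, unnamed factors.
- Kaplan-Meier estimates, log-rank tests and Cox models of PFS and OS with response as a grouping or covariate. These are followed by: "Interaction terms between these factors will also be tested for statistical significance".

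The section labels its analyses as hypothesis generating. It names Fisher's exact test for unadjusted comparisons of response. For biomarker levels in responders and non-responders it names the t-test or Wilcoxon rank sum test and a general linear model. It does not say how the logistic models are to be estimated when responders are few, how many covariates they may hold, or when response status is to be fixed for the PFS and OS comparisons.

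**The concern.** A logistic model of response learns from the rarer outcome. If some combination of covariates splits responders perfectly from non-responders, fully or partly, the data are separated: at least one maximum-likelihood odds ratio is infinite, and its Wald interval and p-value mean nothing. With a handful of responders this can come about by chance alone. A single binary factor with every responder in one level is enough.

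The adjusted results are meant to suggest hypotheses for later trials, and biomarker change is a secondary objective supported by paired biopsies. An infinite or inflated odds ratio is a poor basis for choosing a hypothesis.

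There is a related difficulty with PFS and OS. Response is first assessed at the restaging scan at the end of cycle 2, after treatment has begun. A patient must reach a scan without progression or death to be classed as a responder. Comparing responders with non-responders from the start of treatment therefore favours responders even if response has no bearing on outcome.

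**Working it through.** **Design reproduced.** Inputs are from section 10.1: n1 = 18, continue with at least 1 response, n = 28, positive with at least 3, target 15%. Exact two-stage binomial enumeration gives power 0.803 at 15%. With a null rate of 4% (an assumption within the stated bound), alpha is 0.097 and a minimax search returns this same 18/28 design. At 5%, alpha is 0.158. That is a separate matter. I use 5% as the lower scenario because it is the upper end of the stated range and so the kinder choice here (4% gives 28 × 0.04 = 1.1 responders).

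**Expected responders.**

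- Unconditional: 28 × 0.05 = 1.4; 28 × 0.15 = 4.2.
- Given that stage 2 opens: 18p / (1 − (1 − p)^18) + 10p.
  - 5%: 0.9 / (1 − 0.397) + 0.5 = 2.0
  - 15%: 2.7 / (1 − 0.054) + 1.5 = 4.4

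**Number of responders k, given stage 2.**

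| k | 1 | 2 | 3 | 4 | 5 | 6 | 7 |
|---|---|---|---|---|---|---|---|
| 5% | 0.374 | 0.364 | 0.182 | 0.061 | 0.016 | 0.003 | 0.001 |
| 15% | 0.035 | 0.116 | 0.194 | 0.219 | 0.187 | 0.127 | 0.070 |

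P(1 to 4 responders) is 0.98 at 5% and 0.56 at 15%. P(10 or more) is below 0.001 and 0.006.

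**One binary adjuster, by hand.** If all k responders fall in one level, the odds ratio for that factor is infinite whatever else is in the model.

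- Factor split exactly 14/14: the probability is 2·C(14,k)/C(28,k) = 1, 0.481, 0.222, 0.098, 0.041 for k = 1 to 5. Weighted by the table, this is 0.60 at 5% and 0.17 at 15%.
- Factor present in each patient with probability one half: the probability is about 2^(1−k) = 1, 0.5, 0.25, 0.125, 0.0625. Weighted, 0.61 and 0.19.

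**Two such binary adjusters.** The probability is 1 − (1 − 2^(1−k))² = 1, 0.75, 0.438, 0.234, 0.121, 0.062, 0.031 for k = 1 to 7.

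- 5%: 0.374 + 0.273 + 0.080 + 0.014 + 0.002 = 0.74
- 15%: 0.035 + 0.087 + 0.085 + 0.051 + 0.023 + 0.008 + 0.002 = 0.29

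A continuous biomarker in the same model adds a little to each.

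**Simulation.** Linear-programming check for separation in 28-patient data sets with no true effects, averaged over k given stage 2. Covariates are assumed.

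| Covariates | 5% | 15% |
|---|---|---|
| 1 continuous | 3% | 0.3% |
| 2 continuous | about 10% | about 1% |
| 3 continuous | about 24% | about 4% |
| 1 continuous + 1 binary | about 59% | 18-19% |
| 1 continuous + 2 binary (14/14) | 73% | 26% |
| 2 continuous + 3 binary (14/14) | 82% | 35% |

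Across the checks with one or two binary adjusters the range is about 18-31% at 15% and 59-75% at 5%.

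**Finite fits.** I assumed a true odds ratio of 2 per SD, with one continuous and two binary covariates. At an ORR of about 14%, the finite estimates have median 2.26 and geometric mean 2.95, and 29% lie above 4 or below 0.5. At about 5%, the figures are 2.41, 4.33 and 35%. The centre is moderately inflated and the tail is long.

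**PFS and OS.** No calculation is needed. With about 1 to 4 patients in the responder level, an interaction between response and another factor would often rest on one or two patients in a cell.

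**The case against.** Much of the case for leaving the text alone has force.

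- **Purpose.** The analyses are declared hypothesis generating and the primary ORR analysis does not depend on them. This lowers the stakes. It does not make an infinite estimate useful for forming a hypothesis.
- **Other methods are already planned.** Fisher's exact test, the t-test or Wilcoxon test, and a general linear model with the biomarker as outcome do not suffer logistic separation. The logistic model is a further step, so it would be wrong to infer that an infinite odds ratio would be the trial's biomarker result.
- **The covariates are unknown.** With continuous covariates only, separation at 15% is about 1-4%. It would overstate the case to say that following the plan always breaks the model. Routine adjusters such as sex or RAS status are binary, however, and the text allows any number of them.
- **The estimation method is not stated.** A reader might infer ordinary maximum likelihood with Wald tests. That is the default, but the documents do not say it. What can be shown is that no sparse-data method is specified.
- **The interaction tests.** A reader might attach them to the logistic models and count them as a source of infinite odds ratios. In section 10.2 the sentence follows the Cox models of PFS and OS and precedes the proportional-hazards checks. It concerns hazard ratios, with progressions and deaths as events. Those tests are weak because the responder level is nearly empty, which is a different reason.

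**Conclusion.** The point holds as a gap in section 10.2. Adjusted logistic models of response are committed to in two places, with 2.0 to 4.4 responders expected once stage 2 opens, and nothing in the text protects them against separation. The chance of at least one infinite odds ratio is roughly 18-31% at the 15% target and 59-75% at 5% with one or two binary adjusters, and about 1-4% and 10-24% with two or three continuous covariates only.

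These figures rest on standard maximum likelihood, on assumed covariate sets, on reading the stage 1 rule as at least one response, and on no true covariate effects.

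The use of response as a grouping for PFS and OS without a landmark is a second, separate weakness, argued from the timing of assessment and not from a computed size. Neither weakness touches the primary endpoint or the decision rule. This is an inexpensive improvement to secondary and exploratory analyses, not a flaw in the trial's main conclusion.

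**What to change.** In section 10.2:

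1. State that logistic models of response will use Firth-penalised regression with profile-likelihood intervals, or exact logistic regression with exact intervals. Fit one biomarker at a time, with at most one adjustment covariate, named in advance.
2. State that otherwise the response-by-biomarker analyses stay descriptive or use the exact tests already named. Penalised and exact methods give usable intervals but add no information. For a biomarker split 14/14, the smallest attainable Fisher p-value is 0.48, 0.22 and 0.098 with 2, 3 and 4 responders.
3. For log-rank and Cox comparisons by response, take response status at a landmark, the first restaging scan, and measure PFS and OS from that point.
4. Report the Cox interaction terms as descriptive, without significance tests.

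The cost is wording only: no change to sample size, visits or data collection. There will be fewer adjusted results. Patients with an event before the landmark drop out of that comparison, and a response first seen after the landmark counts as non-response in it. Both should be said when the results are reported.

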1. STUDY SYNOPSIS

| |
|---|
| 
Title of Study: Phase II trial of Nivolumab and Metformin in patients with treatment refractory MSS metastatic Colorectal Cancer
 |
| 
Study Centers: Emory University Winship Cancer Institute
 |
| 
Study Phase: Phase II
 |
| 
Objectives:
 
Primary Objective:
 
▪ The primary endpoint of this study is to Evaluate the effect of metformin in combination with nivolumab on the overall response rate (ORR) (Primary Objective) as assessed by RECIST.1.1 
Secondary Objectives:
 
▪ To determine the effect of the metformin and nivolumab combination on clinical (PFS, OS) outcomes and biochemical (CEA) response.▪ To compare the effect metformin and nivolumab combination on immune and metabolic biomarkers in the tumor microenvironment and systemic circulation (pre and post treatment paired biopsies required). |
| 
Trial Design/Methodology: Single arm phase II study. 28 patients with previously treated (previously treated with fluoropyrimidine, oxaliplatin, irinotecan and EGFR inhibitor – if RAS wildtype) metastatic CRC will be started on metformin and nivolumab combination.
 
Treatment
 
1. Patients will start taking metformin 500 mg po BID for 3 days, then 500 mg am and 1000 mg pm for 4 days, then 1000 mg po bid for 1 week. Patients of the study will get paired biopsies as outlined in study calendar.2. If a patient cannot tolerate metformin 1000 mg po BID the patient will resume the metformin dose which was tolerable3. After 2 weeks of metformin only therapy (lead-in period) patients will start nivolumab 480 mg IV q4 weeks and continue metformin 1000 mg PO BID (or the tolerated dose of Metformin).4. Restaging scans will be performed at the end of cycle 2, then every 8 weeks for 2 years.5. Correlative assays will include- immune profiling of TILs and circulating lymphocytes, plasma cytokine levels and metabolic biomarkers. These will be performed at baseline at baseline, cycle 1 day 1, cycle 1 day 15, Cycle 3 Day 1 and at progression 
Treatment regimen and trial diagram:
 |

Main criteria for exclusion:

- MSI status
- Autoimmune conditions that may require systemic steroids or other immunosuppressive treatments
- Pregnancy or breast feeding

Investigational product and administration:

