6. TREATMENT PLAN

6.1.1 Agent Administration

Treatment will be administered on an outpatient basis. Reported adverse events and potential risks are described in Section 7. Appropriate dose modifications are described in Section 6. No investigational or commercial agents or therapies other than those described below may be administered with the intent to treat the patient's malignancy.

Table 1: Cycle 1 only (Day -14 through 28) Lead-in period

| Regimen Description | | | | | |
|----------------------------|-------------------------------------|-------------|--------------|-----------------|---------------------|
| Agent | Premedications ; Precautions | Dose | Route | Schedule | Cycle Length |
| | | | | | 42 days |

| | | | | | |
|------------|----------------|-----------------------------------|----|------------------------------------|--|
| Metformin | Take with food | 500 mg tablet am, 500 mg pm | PO | Twice daily D-14 through -12 | |
| Metformin | Take with food | 500 mg tablet am, 1000 mg pm | PO | Twice daily D -11 through -8 | |
| Metformin | Take with food | 1000 mg tablet am, 1000 mg pm | PO | Twice daily D -7 through -1 | |
| Metformin* | Take with food | 1000 mg tablet and, 1000 mg pm | PO | Twice daily, D1-28 | |

*If subject cannot tolerate 1000 mg po twice daily, will resume the highest tolerated dose of Metformin.

NOTE: The patient will be requested to maintain a medication diary of each dose of medication (Metformin). The medication diary ([Appendix B](#)) will be returned to clinic staff at the end of each course. Patients with diabetes mellitus will be requested to keep a blood glucose log for the first 4 weeks of the trial ([Appendix C](#))

Table 2: Cycle 2 and subsequent cycles (28 days)

| Regimen Description | | | | | |
|---------------------|------------------------------|------|-------|----------|--------------|
| Agent | Premedications ; Precautions | Dose | Route | Schedule | Cycle Length |

| | | | | | |
|------------|--|--------------------------------|--------------------|--------------------|-------------------|
| Nivolumab | Premedicate with Acetaminophen 650 mg po once prior to Nivolumab, optional | 480 mg | IV over 30 minutes | Day 1 | 28 days (4 weeks) |
| Metformin* | Take with food | 1000 mg tablet and, 1000 mg pm | PO | Twice daily, D1-28 | |

* If subject cannot tolerate 1000 mg po twice daily during Cycle 1, subject will continue the maximum tolerated dose of Metformin as in cycle 1 for the subsequent cycles.

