| Urinalysis | X | | | | | X | | | X | | | X | | | |
| T3, FT4 and TSH | X | | | | X | | | X | | | X | X | X | X | |
| ECG | X | | | | | | | | | | | | | | |

| Trial Period: | Main Study Screening (Visit 2) | Treatment Cycles ^a | | | | | | | | | | End of Treatment | Post-Treatment | | |
|---|--------------------------------|-------------------------------|-----|----------------|----------------|----------------|----------------|----------------|---------|----------------|--------------------------------|---------------------|---------------------------|-------------------------------|--------------------|
| | | 1 ^a | | 2 | 3 | 4 | 5 | 6 | 7 | 8 | To be repeated beyond 8 cycles | | Safety Follow-up | Follow Up Visits ^b | Survival Follow-Up |
| Treatment Cycle/Title: | 1 ^a | D-14 | D-7 | D1 | D15 | | | | | | | Discon | | | |
| Day | | | | | | | | | | | | | | | |
| Scheduling Window (Days): | -28 to -1 | | | ± 3 | $\pm 3^*$ | ± 3 | ± 3 | ± 3 | ± 3 | ± 3 | At time of Discon | 30 days post discon | Every 8 weeks post discon | Every 12 weeks | |
| Tumor Imaging | X | | | | | X ^g | | X ^g | | X ^g | | | | | |
| Newly Obtained Tissue Collection ^h | X | | | X ^h | X ^h | | | | | | | | | | |
| Correlative Studies Blood Collection ⁱ | X | | | X ⁱ | X ⁱ | | X ⁱ | | | | | X ⁱ | | | |

- a. Each cycle is 4 weeks, and there is 14 days lead in period in cycle 1
- b. Only for patients with ongoing treatment related toxicities
- c. Metformin will be taken 500 mg po BID for D-14 to-12, 500 mg am and 1000 mg pm for D-11 to 8, 1000 mg am and 1000 mg pm for D- 7 to -1, and continued 1000 mg BID for the rest of the study (if not able to tolerate 1000 mg BID during D1-14 period subject will be on maximum tolerated dose). Study coordinator will call the patient on Day -13 to confirm the subject is taking the right dose of medication. Nivolumab will be given after biopsy#2 (same day or up to 5 days later), and then repeated every 4 weeks.
- d. ECOG performance status should be done within 14 days or less from day 1 of cycle 1
- e. Lab results from screening may be used if completed within 1 week of day -1
- f. Baseline imaging within 4 weeks of day 1 is acceptable
- g. Scans will be done at the end of cycle 2 (± 3 days), then repeated every 2 cycles (q 8 weeks)

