10.3 Evaluation of Response

All patients included in the study must be assessed for response to treatment, even if there are major protocol treatment deviations or if they are ineligible. Each patient will be assigned one of the following categories: 1) complete response, 2) partial response, 3) stable disease, 4) progressive disease, 5) early death from malignant disease, 6) early death from toxicity, 7) early death because of other cause, or 9) unknown (not assessable, insufficient data). [Note: By arbitrary convention, category 9 usually designates the "unknown" status of any type of data in a clinical database.]

All of the patients who met the eligibility criteria (with the possible exception of those who received no study medication) should be included in the main analysis of the response rate. Patients in response categories 4-9 should be considered to have a treatment failure (disease progression). Thus, an incorrect treatment schedule or drug administration does not result in

exclusion from the analysis of the response rate. Precise definitions for categories 4-9 will be protocol specific.

All conclusions should be based on all eligible patients. Subanalyses may then be performed on the basis of a subset of patients, excluding those for whom major protocol deviations have been identified (e.g., early death due to other reasons, early discontinuation of treatment, major protocol violations, etc.). However, these subanalyses may not serve as the basis for drawing conclusions concerning treatment efficacy, and the reasons for excluding patients from the analysis should be clearly reported. The 95% confidence intervals should also be provided.

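### PFS and OS are compared by response as if response were known at the start, which builds an advantage for responders into the PFS contrast

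*Combined protocol and SAP*

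**What the plan says.** Section 10.2 plans Kaplan-Meier estimates of PFS and OS for "two patient groups stratified by response or other factors will be estimated with the Kaplan-Meier method and compared between different groups", with a log-rank test. Cox models are then used "in the multivariable analyses to assess adjusted effect of response on the" same two endpoints. The section names no landmark, does not say that response counts only from the date it is observed, and gives no time origin for PFS or OS. Time-varying terms appear once, as a conditional remedy: "Violations of the proportional hazards assumptions will be addressed by use of time-dependent covariates or extended Cox regression models". The section also says of its analyses: "The purpose of these analyses is hypothesis generating".

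The timing of response is fixed elsewhere. The synopsis states: "Restaging scans will be performed at the end of cycle 2, then every 8 weeks for 2 years". Footnote g of the study calendar (section 7) agrees: "Scans will be done at the end of cycle 2". Table 1 in section 6.1.1 is headed "Cycle 1 only (Day -14 through 28) Lead-in period", so cycle 1 includes a 14-day metformin lead-in. Section 10.3 counts progressive disease and early death as treatment failures, and section 10.4 puts everyone who received any study drug into the efficacy evaluation.

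**The concern.** Response is an outcome that can first be seen at the end of cycle 2. If patients are sorted by eventual response and followed from the start of treatment, responders cannot have an event before that scan, because an event would have made them non-responders. The event-free time that responders had to complete is credited to response, and every early progression or death is charged to the other group. This is immortal-time bias, and it arises even when response has no bearing on what happens afterwards.

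If responses occur, the curves, the log-rank test and the adjusted hazard ratio would all show longer PFS in responders. Section 10.2 intends its results to supply hypotheses for later trials, so an artefact of the grouping could be carried forward as a finding.

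**Working it through.** The plan gives no hazard ratio, event count or power for this contrast, so there is no figure to reproduce. The check asks what the planned analysis returns when response is unrelated to later outcome (true hazard ratio 1.0).

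**1. Earliest date of response.** From cycle 1 day 1: 28 + 28 = 56 days (56/30.44 = 1.84 months). From the first metformin dose: 14 + 28 + 28 = 70 days (2.30 months).

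**2. Where the early events go.** Assumed, because the documents give no medians: independent exponential times, OS median 6, 8 or 10 months, progression median 2 or 3 months.

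P(event-free at first scan) = exp[-(ln 2/OS median + ln 2/progression median) x 1.84]

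- OS 10, progression 3: exp(-0.300 x 1.84) = 0.575, so 42% (about 12 of 28) have failed by the first scan.
- OS 8, progression 3: exp(-0.318 x 1.84) = 0.557, so 44% (12.4 of 28) have failed.
- OS 6, progression 2: exp(-0.462 x 1.84) = 0.427, so 57% (16 of 28) have failed.

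The 15% target in section 10.1 gives 0.15 x 28 = 4.2 responders. In the middle case, if group membership carried no information about early events, responders would have 12.4 x 4.2/28 = 1.9 of them. By construction they have none.

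**3. Hazard ratio for response as planned.** Simulation with 400,000 patients per scenario. Progression is dated at the next 8-weekly scan, and response is assigned at random among patients alive and progression-free at week 8, at 15% overall. Efron and Breslow are two ways of handling tied event dates.

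| Setting | PFS HR (truth 1.0) |
|---|---|
| Base case, Efron ties | 0.45-0.58 |
| Base case, Breslow ties | 0.51-0.62 |
| Progression dated continuously | 0.45-0.58 |
| Progression median 4 months, OS 8-10 (Efron) | 0.62-0.63 |
| Clock at first metformin dose (Efron) | 0.38-0.51 |
| 30% of responses first seen at week 16 (Efron) | 0.36-0.50 |
| Virtually no deaths before progression (Efron) | 0.54-0.65 |

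In the base case, apparent median PFS is 3.7-5.5 months in responders and 1.8-2.0 in non-responders. Among patients still progression-free after the first scan, the two medians differ by at most 0.05 month. A separately built simulation, with median PFS 2-4 months and two models for death, gave 0.46-0.68.

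For OS the hazard ratio is 0.78-0.84 in the base case and 0.73-0.79 with later responses. It is 0.71-0.81 in a model where the risk of death depends on progression; part of that last figure is a real association, since the time-dependent hazard ratio there is 0.81-0.91.

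**4. The test at n = 28.** The trial stops at 0 responses in 18, and a comparison needs at least 2 responders. P(fewer than 2) = (1-p)^18 + 18p(1-p)^27.

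- p = 0.15: 0.054 + 0.034 = 0.087 (unrounded terms), so 91% of trials have at least 2. In these the two-sided 5% PFS log-rank test rejects in 14-33%, all favouring responders. With exactly 3 responders, the smallest positive result, it rejects in 8-20%. At a 4-month progression median it rejects in about 9-12% of trials with at least 2 responders.
- p = 0.05: 0.397 + 0.225 = 0.623, so 62% of trials have fewer than 2. The rest reject in 6-13%.
- OS at p = 0.15: 4-5%, the nominal level.

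**5. Would the proportional-hazards clause catch it?** An approximate residual test at n = 28 flagged non-proportionality in only 6-14% of simulated trials. Even when triggered, the clause changes the Cox model and leaves the curves and the log-rank test as they are.

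**6. After correction.** If response counts strictly after its scan, or if the landmark excludes patients whose progression is dated at that scan, the PFS hazard ratio is 1.00-1.01. Without that same-scan rule it stays at 0.52-0.64 (Efron) or 0.60-0.69 (Breslow), and the test rejects in 10-22%.

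**The case against.** The best defence is scope. The contrast is one use of a general clause in analyses declared hypothesis generating, and it touches neither the ORR decision nor the single-arm PFS and OS estimates. If the true ORR is near the historical 5%, most trials will have nothing to compare; over all trials at that rate, false significance occurs in about 2.4-4.6%. These points stand, and they keep this a secondary matter.

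The size also depends on assumed medians. It shrinks as progression slows (step 4 at 4 months), and the gap between PFS and OS narrows when death follows progression closely; the closest case was 0.68 against 0.71. That stands too, but no scenario removed the PFS bias in the hazard ratio.

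The plan never states that response is a baseline factor. However, curves and a log-rank test on response groups, with no landmark, treat it as one.

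The efficacy set is less settled than section 10.4 suggests. Sections 6.12 and 8.1.1.6 make some treated patients inevaluable for the primary endpoint and replace them, and section 8.1.3.1 replaces those who refuse the second biopsy. The first two rules exempt patients who stop because of progression, so early progressors stay in the non-responder group and the mechanism survives.

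Finally, a landmark leaves very few patients. That is true, and it is why the corrected contrast should be descriptive.

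**Conclusion.** The concern holds. The existence and direction of the PFS bias follow from the planned grouping and the scan schedule; only its size rests on assumptions. With a progression median of 2-3 months, an OS median of 6-10 months and 15% responders, a response with no effect would appear to cut the PFS hazard by roughly 40-55%. Across the other settings tried, the spurious hazard ratio ran from 0.36 to 0.68. False-positive PFS tests become common at the target response rate and are much less of an issue near 5%. For OS the estimate is biased but the test stays near its nominal level. The problem arises only if responses occur and is confined to the responder contrast.

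**What to change.** - **Origin.** Define the time origin for PFS and OS.
- **Cox models.** Code response as time-dependent, switching on strictly after the date of the scan that shows it, with each responder's follow-up split at that date. Name the tie method, because scan-dated progressions are heavily tied.
- **Curves.** Replace the by-response Kaplan-Meier curves and log-rank test with a descriptive landmark at the first restaging scan. For PFS, include patients alive and progression-free after that scan, excluding those whose progression is dated at it. For OS, include patients alive at the landmark. Report how many are excluded and how many respond later.
- **Unchanged.** Keep the single-arm Kaplan-Meier estimates as planned.

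**Cost.** This is re-analysis of data already collected, with no new patients or visits. Under the base-case assumptions the landmark drops 12-16 of 28 patients for PFS (8-12 of them with progression dated at the first scan) and 3-5 of 28 for OS. About 4 responders then face 8-12 non-responders for PFS. The corrected PFS test rejects in 6-7% of trials (2.1-2.5% favouring responders), and the separate simulation put the landmark test at 8-9%. Give hazard ratios and intervals descriptively, without p-values.

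**Two related clarifications, separate from the bias.** Section 10.2 censors both PFS and OS at last follow-up, although imaging follow-up (section 8.1.7) and telephone survival follow-up (section 8.1.7.1) are different phases. State that PFS is censored at the last adequate tumour assessment, before any new anti-cancer therapy started without progression, and OS at last contact. Footnote b of the study calendar limits follow-up visits to patients with unresolved treatment toxicity, whereas section 8.1.7 has everyone who stops without progression imaged; these passages must be reconciled.
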